7. Have not participated in a smoking study, other than phone survey, in last 3 months
8. Able to complete a survey on a computer
9. Able to complete a survey in English
10. Able to complete surveys delivered via email
11. Able to complete 3, 20-minute, surveys
12. Able to complete a 5-min survey each morning for 15 days
13. Lives in the US

Experimental Conditions

- Optimal Group: receive the risk and constituent messages with optimized source depiction and engagement formats.
- Suboptimal Group: receive the risk and constituent messages without source or engagement text.
- Control Group: receive littering messages

Allocation and Blinding

Participants will not be informed specifically about the possible interventions that they may be assigned to. Researchers will not be blinded to the condition that participants had been assigned to, however all outcome measures will be assessed via online survey.

At the end of the baseline survey, survey software will randomly assign participants to one of the three study arms. Participants will have an equal chance of being randomized to each study arm.

Messages

Constituent Message	Words (Characters)	Littering Message	Words (Characters)

CIGARETTE SMOKE CONTAINS URANIUM THIS CAUSES LUNG TUMORS AND KIDNEY DAMAGE
 	11 (76)	
PLEASE REFRAIN FROM LITTERING CIGARETTE BUTTS ARE THE MOST LITTERED ITEM
 	11 (74)

CIGARETTE SMOKE CONTAINS ARSENIC THIS CAUSES HEART DAMAGE
 	8 (59)	
CIGARETTE BUTTS DON'T BIODEGRADE PLEASE DO NOT LITTER
 	8 (55)

CIGARETTE SMOKE CONTAINS FORMALDEHYDE THIS CAUSES THROAT CANCER
 	8 (65)	
CIGARETTE LITTER REQUIRES CLEANUP DISCARD CIGARETTE BUTTS PROPERLY
 	8 (68)

[figure not shown]

CIGARETTE SMOKE CONTAINS LEAD THIS CAUSES CANCER AND BRAIN DISORDERS
 	
10 (70)
	
CIGARETTE LITTER POLLUTES THE EARTH DISPOSE OF CIGARETTE BUTTS CORRECTLY
 	
10 (74)

CIGARETTE SMOKE CONTAINS AMMONIA THIS CAUSES BREATHING PROBLEMS
 	
8 (65)
	
CIGARETTE BUTTS ARE POLLUTION PLEASE REFRAIN FROM LITTERING
 	
8 (61)

Study Flow

Pilot: Assess whether we can proceed and launch the full study when they have completed post-test 1, allow pilot participants to complete the full study (through post-test 2).

Full Study: Baseline survey, then a survey every morning for 15 days assessing previous day behavior and delivering a message. Follow up with post surveys at day 16 and 32.

Process:

Days 1-15: Morning Surveys

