- *Cigarette littering message (Control)*: Messages about littering cigarettes will include text designed to discourage people from littering their cigarette butts, and an image related to the message. Each condition has 5 messages that will be repeated 3 times in a counterbalanced order. Study investigators used text developed by

investigators associated with our Center for Regulatory Research on Tobacco Communication. Design of these messages was developed by our team.

Randomization

At the end of the baseline survey, survey software will randomly assign participants to one of the three study arms. Participants will have an equal chance of being randomized to each study arm.

Sample Size

Sample Size Background:

Our study is examining the difference in quit intention for participants that receive 1) Optimal constituent messages with quitline information, and self-efficacy information, or 2) Sub-optimal constituent messages or 3) Messages about littering cigarette butts.

[figure not shown]
No studies from the literature that we could find examined difference in quit intention or quitting behaviors by optimal text vs. sub-optimal warning text vs. control in a warning or smoking communication context.

In a meta-analysis by Noar et al. 2014 (Pictorial cigarette pack warnings: a meta-analysis of experimental studies) the effect size between pictorial vs. text only warnings on intention to quit smoking was $d=0.54$. Other outcomes ranged between effect size $d=-0.03$ (recall of warning text), and $d=1.82$ (intention not to start smoking).

Assumptions for the power calculation:

- The smallest effect size between our groups will be between the optimal and sub-optimal group. If we can see a difference between these groups, we will be able to see the larger effects that we expect between the other groups.
- We will be using a continuous measure of quit intention (or treating quit intention as a continuous variable, and collecting it as a categorical response).
- The effect size on quit intention is likely to be smaller for added self efficacy and quit line text than for added pictorial images.
- To be conservative, we will use a one time measure to calculate power, repeated measures would add power to this analysis (decrease necessary sample size).
- We will use the d statistic to see what group size would have to be enrolled, and compare two means (optimal and sub-optimal) with a t-test

Based on these assumptions:

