Gay, lesbian, or bisexual								
Current Cigarette Smoking								
Current smoker								
Nonsmoker								
Fagerstrom Nicotine Dependence Score (FTND)								
Trust in FDA								
Number of Times Participants Viewed a Message During Follow Up								

To update Table 1 see 'Table 1 V1.xlsx' in Analysis Plan folder

Analysis

Outcome definitions

- Quit intentions [Time Frame: day 16] PRIMARY OUTCOME
 - 3 item measure with high reliability, average of the 3 items to create a score range 1-4 (Brewer et al., 2016, 2018; Klein, Zajac, & Monin, 2009)
 - We will compare the differences between pre and post
- Number of cigarettes smoked each day [Time Frame: Measured daily on days 1-15]
 - Continuous, Modified from FTND (Heatherton, Kozlowski, Frecker, & Fagerström, 1991; Storr, Reboussin, & Anthony, 2005)
- Number of cigarettes forgone each day [Time Frame: Measured daily on days 1-15]
 - Continuous, adapted from Brewer 2016 (Brewer et al., 2016)
 - May be zero inflated, if yes, may choose to dichotomize to 0/1
- Number of cigarettes butted out each day [Time Frame: Measured daily on days 1-15]
 - Continuous, adapted from Brewer 2016 (Brewer et al., 2016)
 - May be zero inflated, if yes, may choose to dichotomize to 0/1
- Quit attempts during the study [Time Frame: Measured on days 16 and 32]
 - Adaptation from Fagan (Fagan et al., 2007)
 - May be zero inflated, if yes, may choose to dichotomize to 0/1
- Awareness of quitline [Time Frame: Measured on day 16]
- Recall of quitline phone number [Time Frame: Measured on day 16]
- Use of the quitline during the study [Time Frame: Measured on days 16 and 32]
- Intention to use the quitline [Time Frame: Measured on days 16 and 32]
- Quit intentions [Time Frame: Measured on day 32]
 - 3 item measure with high reliability, average of the 3 items to create a score range 1-4 (Brewer et al., 2016, 2018; Klein et al., 2009)
 - We will compare the differences between pre and post
- Self Efficacy [Time Frame: Measured on days 16 and 32]

- 1 item (“IARC HANDBOOKS OF CANCER PREVENTION,” n.d.; Thrasher, Swayampakala, Borland, et al., 2016; Thrasher, Swayampakala, Cummings, et al., 2016)
- Response Efficacy [Time Frame: Measured on days 16 and 32]
 - 1 item (Thrasher, Swayampakala, Cummings, et al., 2016)

Analysis Methods

Analysis methods will depend on the time point that the outcome was measured. Post test measures will be analyzed differently than measures from the daily surveys, as outlined below.

Post test measures

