Daily Questionnaire Measures

What analysis method will be used and how treatment effects will be presented

Mixed models to account for repeated measures of the same participant.

Any adjustment for covariates

Covariates included in the analysis model (in addition to treatment group):

- Dose of ads (# of times participants viewed a message)

Methods used for assumptions to be checked for statistical methods

Linear mixed model is an extremely flexible for modeling continuous outcomes. It turns out that linear mixed models are robust to violations of some of their assumptions. The followings are the assumptions for linear mixed model: 1) Independent (The outcomes of different people are assumed to be statistically independent of each other.) Note: the outcomes within a person are correlated. 2) Normality (random effects are assumed to be normally distributed with mean zero and the residuals are normally distributed.)

Details of alternative methods to be used if distributional assumptions do not hold (eg normality, proportional hazards, etc)

Because mixed models are robust to violations of some of their assumptions, we do not anticipate needing to use an alternative method.

Any planned sensitivity analyses for each outcome where applicable

None a priori

Any planned subgroup analyses for each outcome including how subgroups are defined

None a priori

Missing Data

Mixed models are appropriate to use and robust to missing data, so we will be able to include everyone who completed at least 1 daily questionnaire.

Additional Analyses

None a priori

Harms

Adverse events were not expected in this trial due to the minimal risks to participants, and no threat to participant health, so this section is not applicable.

Statistical Software

Statistical analyses will be conducted in SAS 9.4 (Cary, NC)

References

Final Dataset: rct_combined_07232018 [location removed]

Data Cleaning Syntax: 01_Create_Analytic_Files.sas [location removed]

Study Protocol: RCT_Protocol_V5 [location removed]

[figure not shown]
Analysis plan compiled according to “Guidelines for the Content of Statistical Analysis Plans in Clinical Trials” (Gamble et al., 2017)

- Brewer, N. T., Hall, M. G., Noar, S. M., Parada, H., Stein-Seroussi, A., Bach, L. E., ... Ribisl, K. M. (2016). Effect of Pictorial Cigarette Pack Warnings on Changes in Smoking Behavior: A Randomized Clinical Trial. *JAMA Internal Medicine*, *176*(7), 905–912. <https://doi.org/10.1001/jamainternmed.2016.2621>

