Behavior Instructions	Please think about yesterday		Behav_Inst	Behav_Inst	Behav_Inst
	What time did you wake up yesterday?	Time	Time#1_Wake_Hour Time#1_Sleep_Hour Time#2_Wake_Min Time#2_Sleep_Min Time#3_Wake_AMPM Time#3_Sleep_AMPM		
	What time did you go to sleep last night?	Time			
Behavior ⁴	How many times yesterday did you dispose of your cigarette butts by dropping them on the ground?	Dropdown list 0-100, 101=refused	Lit1	Lit1	Lit1
	How many times yesterday did you dispose of your cigarette butts by throwing them or dropping them out of the car window?		Lit2	Lit2	Lit2
	How many times yesterday did you stop yourself from having a cigarette because you wanted to smoke less?		Forgo	Forgo	Forgo
	How many times yesterday did you butt out a cigarette before you finished because you wanted to smoke less?		Butt	Butt	Butt
PAGE BREAK					
Cigarettes Smoked ⁷	Yesterday, from the time you woke up until noon, how many cigarettes did you smoke?	Dropdown list 0-100, 101=refused	Cigs_Morn	Cigs_Morn	Cigs_Morn

Construct (Source)	Question Text	Response Option	Pretest Var Name	Post 1 Var Name	Post 2 Var Name
	Yesterday, from noon until you went to sleep, how many cigarettes did you smoke?		Cigs_Afternoon	Cigs_Afternoon	Cigs_Afternoon
PAGE BREAK					
Thinking Instructions ⁴	Overall yesterday, how much did you...		Think	Think	Think
Thinking About Chemicals ⁴	Think about the chemicals in the smoke from your cigarettes?	5=All of the time 4=Often 3=Sometimes 2=Rarely 1=Never	Think_Chem	Think_Chem	Think_Chem
Thinking About Risks	Think about the harm your smoking might be doing to you?		Think_Risk	Think_Risk	Think_Risk
Thinking About Littering	Think about discarding cigarette butts properly?		Think_Lit	Think_Lit	Think_Lit
Thinking about quitting	Think about quitting smoking?		Think_Quit	Think_Quit	Think_Quit
PAGE BREAK					
StudyInfo1	The next few pages give you some more information for what to expect during the study.		StudyInfo1		
PAGE BREAK			PAGE BREAK		
StudyInfo2	Starting tomorrow, you will receive an email at 7am every morning for 15 days from [contact]', with a link to a short survey. You have until 11am to open the link and answer the survey, or you will have to wait until the next one is sent. 		StudyInfo2		
PAGE BREAK			PAGE BREAK		

Construct (Source)	Question Text	Response Option	Pretest Var Name	Post 1 Var Name	Post 2 Var Name

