	How many times yesterday did you stop yourself from having a cigarette because you wanted to smoke less?		Forgo
	How many times yesterday did you butt out a cigarette before you finished because you wanted to smoke less?		Butt
PAGE BREAK			
Cigarettes Smoked ⁷	Yesterday, from the time you woke up until noon, how many cigarettes did you smoke?	Dropdown list 0-100, 101=refused	Cigs_Morn
	Yesterday, from noon until you went to sleep, how many cigarettes did you smoke?		Cigs_Afternoon
PAGE BREAK			
Thinking Instructions ⁴	Overall yesterday, how much did you...		Think
Thinking About Chemicals ⁴	Think about the chemicals in the smoke from your cigarettes?	5=All of the time 4=Often 3=Sometimes 2=Rarely 1=Never	Think_Chem
Thinking About Risks	Think about the harm your smoking might be doing to you?		Think_Risk
Thinking About Littering	Think about discarding cigarette butts properly?		Think_Lit
Thinking about quitting	Think about quitting smoking?		Think_Quit

Construct (Source)	Question Text	Response Option	Var Name
PAGE BREAK			
Instruction	Please view the message on the next screen. After 10 seconds, you will be able to click the '>>' to move forward to the next page. [Messages should appear at the top of the screen for all subsequent questions]		Morn_Inst1
Page Break			
Message	Condition 1 or 2(Arsenic, Formaldehyde, Uranium, Ammonia, Lead) Or Control Messages [This should appear on the screen for 10 seconds before participants are able to move on to questions on the next page]		Message
Page Break			
Affect Instruction	How much did the message make you feel...		Affect_Inst
Affect ²⁵⁻²⁷	Anxious?	5=Extremely 4=Very 3=Somewhat 2=A little 1=Not at all	Affect_1
	Sad?		Affect_2
	Scared?		Affect_3
	Guilty?		Affect_4
	Disgusted?		Affect_5
Page Break			
Credibility ²⁸	Please indicate how much you think the message is...		Cred_Inst
	Accurate	7 = Very accurate 1 = Not very accurate	Cred_1
	Authentic	7 = Very authentic 1 = Not very authentic	Cred_2
	Believable	7 = Very believable 1 = Not very believable	Cred_3
Page Break			

Construct (Source)	Question Text	Response Option	Var Name
Instruction	Please select the bubble to show how much you agree or disagree with the statements below:		PE_Inst
Perceived Effectiveness ²⁹	The message makes me concerned about the health effects of smoking.	5=Strongly agree	PE_1
	The message makes smoking seem unpleasant to me.	4=Somewhat agree	PE_2

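### The day-1 morning report describes behaviour before any message, yet days 1-15 all count as daily outcome; a pooled arm effect would be about 1/15 too small

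*Combined protocol and SAP*

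**What the plan says.** **Timing.** Study Flow describes a "Baseline survey, then a survey every morning for 15 days assessing previous day behavior and delivering a message". Both Allocation and Blinding (protocol) and Randomization (SAP) state: "At the end of the baseline survey, survey software will randomly assign participants to one of the three study arms". At the end of the pre-test, Appendix A tells participants: "Starting tomorrow, you will receive an email at 7am every morning for 15 days".

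**Order within a morning survey.** The Morning Questionnaire in Appendix A opens with the previous-day behaviour items, for example "Yesterday, from the time you woke up until noon, how many cigarettes did you smoke". The instruction "Please view the message on the next screen" comes only after these items and the questions on thoughts.

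**Outcome and model.** Outcome definitions lists "Number of cigarettes smoked each day [Time Frame: Measured daily on days 1-15" and gives cigarettes forgone and butted out the same window. For those two counts it adds: "May be zero inflated, if yes, may choose to dichotomize to 0/1". Under Daily Questionnaire Measures the method is "Mixed models to account for repeated measures of the same participant". Besides treatment group, the only listed covariate is dose, the number of times a message was viewed. Anyone with at least one completed daily survey is included. Timing of Outcome Assessments shows that the pre-test also collects the previous-day behaviour items.

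**The concern.** The first of the 15 daily records cannot carry an effect of the messages, because none has yet been shown. The SAP does not map survey day to behaviour day, set the first record aside or use it as baseline. An analyst who follows the outcome window and the listed terms would enter it as a treated outcome.

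This would pull the estimated effects on all three daily behaviour outcomes toward zero. A person who completed only the day-1 survey would enter the analysis with pre-message behaviour alone. The stakes are limited to secondary outcomes.

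**Working it through.** The plan gives no figure for this point. Its only sample-size result, 253 per group for d = 0.25, concerns quit intention. It reproduces (the t-test solution is 252.13, rounded up to 253; 3 × 253 = 759) but has no bearing here.

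**Step 1: map survey day to behaviour day.** Call the day of the baseline survey day 0. Morning survey *s* asks about day *s* − 1.
- Survey 1 covers day 0. Its items come before the first message, so the true arm effect is 0. If enrolment in the survey system delayed the start, the report would still precede any message.
- Surveys 2-15 cover days 1-14, all of which include time after the first message.

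**Step 2: pooled arm effect.** Assume a linear model, a random intercept, complete surveys and one arm term. Each record then has weight 1/15. With average post-message effect Δ over surveys 2-15:

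estimate = (1 × 0 + 14 × Δ)/15 = 0.933Δ, a loss of 1/15 = 6.7%.

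Under equal weights this holds for any shape of effect over the 14 days. A day main effect shared by the arms does not remove it. Nor does dose: with complete surveys, dose is the same in every arm on each day, whether it is a total or a running count.

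**Step 3: sensitivity to what the documents leave open (all values assumed).**

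| Departure from step 2 | Loss |
|---|---|
| AR(1), correlation 0.3 / 0.5 / 0.7, constant effect | 9.0 / 11.8 / 16.9% |
| AR(1), same correlations, effect building linearly | 6.7% at each |
| Surveys missed at random, 90 / 80 / 60% completed | 7.5 / 8.5 / 11.7% |
| Dichotomised, control log-odds −1 or 0 | 6.3 to 7.6% |
| Dichotomised, control log-odds −3 (mostly zeros) | 5.0 to 6.2% |

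- *AR(1).* The first-day weight is 1/(2 + 13(1 − ρ)); at ρ = 0.5 this is 1/8.5 = 0.118. Under a constant effect that weight is the loss. The weights are symmetric over the 15 days. An effect rising linearly from 0 to 1 is therefore estimated as 7/14 = 0.500, against a post-message average of 7.5/14 = 0.536. The ratio is 0.933 for every ρ.
- *Missed surveys.* A person who missed day 1 usually reports pre-message behaviour at the first completed survey. With *m* completed surveys the share kept is (*m* − 1)/*m*, averaged over *m* ~ Binomial(15, p) with random-intercept weights (intraclass correlation 0.7). The figures assume that nobody saw a message in an unfinished survey. If everyone who missed day 1 had already seen one, the loss returns to 6.7%.
- *Dichotomised.* A random-intercept logistic model with a pooled arm term was fitted to the large-sample distribution, with arm log-odds ratio 0.3 to 1.0 and intercept SD 1 or 2. The loss is on the log-odds scale.

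**Step 4: cost of dropping one day.** The variance of a person's mean over *k* days is proportional to ICC + (1 − ICC)/*k*.
- ICC 0.7: 0.7214 (14 days) against 0.7200 (15 days), ratio 1.002.
- ICC 0.5: 0.5357 against 0.5333, ratio 1.004.

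**The case against.** **The model is not fully stated.** The SAP names no day term, arm-by-day term, covariance structure or contrast. Day-specific contrasts from day 2 onward in an arm-by-day model would not be diluted. The window can also be read as saying when the measurement is taken, and the protocol openly says that the surveys assess the previous day. This stands in part: the 6.7% is conditional on pooling. But no day-by-arm term is listed and nothing turns survey day into behaviour day, so a pooled arm term is the plain reading.

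**A larger bias is tempting to claim.** A reader might infer losses of 9 to 17% from serial correlation. The documents do not support this, because those losses need a constant effect from the first message as well as AR(1) errors. With a linearly building effect the loss is 6.7% at each correlation tried; with a fading effect it would be larger. Neither covariance nor effect shape is given. Nor is there one exact figure for a dichotomised outcome: the case that would prompt dichotomising, many zeros, gives a slightly smaller loss.

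**It is minor.** Only secondary outcomes are affected, and the plan sets no power target for them. This stands as to size. It does not justify leaving a known pre-message record among the treated outcomes when re-indexing removes it.

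**Conclusion.** The point holds. By the documents' own survey order, the day-1 report precedes any message, while the stated window and listed model terms treat it as outcome data. With a pooled arm effect, a linear random-intercept model and complete surveys, the three daily behaviour effects are estimated at about 14/15 of the average post-message effect, about 6.7% too small. Other covariance structures, effect shapes, missed surveys or dichotomisation would shift that figure, and the documents do not fix them.

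A reader might infer that the trial's main conclusion is at risk or that false positives become more likely. Neither follows. The primary outcome is quit intention at day 16, which does not use these records. If the messages have no effect, a record with no arm difference adds no bias, so type I error is unaffected.

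**What to change.** Issue a dated SAP revision whose rationale rests on survey design:

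1. Define behaviour day as survey day minus 1 and estimate the arm effect from mornings 2-15 only. Do not count the day-1 report as a treated outcome: either drop it, or keep it as a pre-treatment row with the arms constrained equal. Choose one and say so.
2. Adjust for the matching pre-test previous-day item, which is collected before randomisation. Any precision gain depends on a correlation that the documents do not give, so none is claimed.
3. State that people with only the day-1 survey contribute no post-message outcome data, and state that the arm contrast is pooled over days.
4. For people who missed day 1, treat the first completed survey as pre-message in a sensitivity analysis. If day 1 is simply dropped, up to 0.8 / 1.8 / 5.0% dilution remains at an assumed 90 / 80 / 60% completion. The message sits mid-survey, so some people may have seen one in an unfinished survey; the documents do not say whether that is recorded.
5. Report the days 1-15 version alongside.

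**Cost.** No new data. Dropping day 1 gives one fewer outcome day, about 0.2 to 0.4% more variance of a person's mean at an assumed ICC of 0.7 to 0.5. The change must be disclosed as made after the dataset existed: the SAP is dated 24 July 2018 and cites a final dataset labelled 07232018. Researchers are not blinded, and the change is expected to move estimates away from zero. Item 5 keeps that visible.
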